#### TRIAL SIZE:

1500 RCS each consisting of multiple patients randomized 1:1 to control and intervention arms

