#### Hypotheses

Primary:

 The intervention results in a greater proportion of immediate ambulance responses in RCS being directed to the patient in the most critical condition as operationalized by subsequent NEWS value.

Secondary:

- The intervention improves differentiation with regards to a composite risk score consisting of ambulance interventions, abnormal initial ambulance findings, emergent transport, hospital admission, and mortality between patients receiving immediate vs. delayed ambulance response during RCS.
- 2. The intervention improves differentiation regarding NEWS between patients receiving immediate vs. delayed ambulance response during RCS.

Other pre-specified analyses:

- 1. Evaluation of overall personnel compliance with risk assessment instrument in intervention arm.
- 2. Evaluation of compliance in intervention arm cases where the model had a high vs low level of confidence.
- 3. Evaluation of improved/degraded compliance with risk assessment instrument over time as manifested by a slope change in a time series analysis of intervention group
- 4. Evaluation of spillover effects as manifested by a significant positive slope in a time series analysis of control group outcomes
- 5. Evaluation of change in risk assessment tool predictive value over time (covariate drift)
- 6. Evaluation of model calibration with regards to age, gender, and complaint category

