#### Flow

Prior to initiation of the study, the risk assessment tool will be integrated into the dispatching interface used by all study centers. Ambulance directors will have overall responsibility for executing the study protocol, and be tasked with identifying RCS suitable for inclusion in the study.

Patients are included in the study upon the identification of an RCS involving eligible patients by the ambulance director at the point in time when an ambulance is available for immediate dispatch to one of the patients. Directors are instructed to carefully consider any non-clinical factors relevant to prioritizing the patients prior to randomization, and exclude any RCS where these factors would override a clinical determination per the above exclusion criteria. Upon selecting the relevant patients and pressing a button in the interface to compare the selected patients, the RCS will be randomly assigned to a study arm. In the control arm, the risk scores for each patient will be calculated and stored, but not displayed to the user. In the intervention arm, a mark will be displayed in the interface indicating which of the included patients has the highest risk score, along with a color-coded indicator of model confidence.

In both study arms, the ambulance director will confer with the nurses involved in triaging the patients to confirm which patient should receive the available ambulance. In the intervention arm, the ambulance director will note which patient was proposed by the machine learning framework in conference with the nurses. The director will then dispatch the available ambulance to the patient determined through this process to have the greatest need. This process will be repeated each time an ambulance becomes available.

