## Sample Size

Given the prevalence and diversity of non-clinical determinants in resolving RCS, the actual retrospective accuracy of dispatchers in identifying the most critically ill patients could not be determined. Instead, sample size was determined using a simulation-based approach. Low-priority calls are divided into 2 categories – 2A and 2B. A simulation was performed under the assumption that a priority 2A call would always be selected for immediate ambulance dispatch over a priority 2B call, and that dispatchers would have 100% compliance with the machine learning tool.

Based on 1000 bootstrap resampled pairs of patients ranked using either dispatch category or the ML framework, a U-statistic of 0.545 in favor of the ML framework was identified. This resulted in required sample size of 1500 at  $\alpha$ = 0.05,  $\beta$  = 0.85, and a randomization ratio of 1:1 for a Wilcoxon–Mann–Whitney test of difference in central tendency. (12) Based on an estimate of 2 RCS per day meeting all inclusion criteria, an upper bound on the data collection duration was set to 2 years.

Upon further refinement of the prediction models over the course of the pilot study, it was found that this difference-based test had an excess of power, and a more conceptually simple but less sensitive formulation of the primary hypotheses was adopted. Pilot study data indicate that RNs direct the available ambulance to the patient with the highest NEWS score 63.5% of the time (considering ties as "correct" assessments), while simulations suggest that the model will mark the patient with the highest NEWS correctly in 70.3% of cases, resulting in an estimated power of 0.8 at n=1500 using a two-sided test of proportions.

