## Statistical analysis

To generate risk predictions, gradient boosting models are applied to patient demographics, structured CDSS data, and free-text noted embedded using the bag-of-words method. The methods are implemented in the openTriage platform as the 'uppsala\_alitis' framework (13) and have been validated in previous research.

The primary hypotheses will be evaluated using a standard two-sided test of proportions between the intervention and control groups. Investigating the secondary hypotheses will involve comparing outcomes for the patient receiving an ambulance immediately with patients for whom dispatch is delayed. Patients who do not receive an ambulance immediately may also potentially be included in later trials. This induces a potential that information from intervention arm comparisons could be used by dispatchers in control arm comparisons, thus biasing the results in the direction of a smaller intervention effect. Steps were taken in the development of the user interface to limit these "spillover" effects.

Figure 1 – Analysis flow

Additional pre-specified analyses 1-2 will be investigated by assessing the compliance of dispatchers with the risk assessment tool of risk scores in the high and low confidence groups of the intervention arm (calibrated based on pilot study data to consist of ca. 50% of assessments each), as well as dispatcher compliance, with the hypothesis that compliance will be higher in the high-confidence group.

Pre-specified analyses 3-5 will be examined using time-series analysis within a regression framework employing a variable representing the study month as the independent variable of interest. Analysis 6 will be conducted by constructing calibration curves for the risk model based on the patient groups of interest.

Missing vital sign data will be imputed using Multivariate imputation by chained equations. (14) As we found previously that between-imputation variance after calculating NEWS scores was minimal, the median of 5 imputed NEWS values will be used to assess the primary hypothesis. An analysis of loss to follow-up (i.e., patients requesting to withdraw from the study) will be performed.

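### The spillover analysis tests for a rising trend in control-arm outcomes, which has only about 21% power even if spillover becomes complete, so a non-significant slope says little

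*Combined protocol and SAP*

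**What the plan says.** Hypotheses, item 4 of the other pre-specified analyses: "Evaluation of spillover effects as manifested by a significant positive slope in a time series analysis of control group outcomes". Statistical analysis adds the method: "Pre-specified analyses 3-5 will be examined using time-series analysis within a regression framework employing a variable representing the study month". For this analysis the plan gives no alpha, power, effect size or interval, and no rule for reading a null result.

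Statistical analysis also explains the threat. A patient who is passed over may enter a later comparison, so what dispatchers saw in an intervention-arm RCS can reach a control-arm RCS and shrink the estimated effect. It says the interface was designed to limit this.

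Two other places bear on the point. Flow: "In the control arm, the risk scores for each patient will be calculated and stored, but not displayed to the user". Sample Size gives the planning rates. For the nurses in the pilot: "RNs direct the available ambulance to the patient with the highest NEWS score 63.5% of the time". For the tool: "the model will mark the patient with the highest NEWS correctly in 70.3% of cases". The same section puts the power of the primary test on these two rates at 0.8 with 1500 RCS, two-sided.

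**The concern.** Spillover means that control-arm dispatchers begin to choose as the tool would. Item 4 looks for this only through its effect on control-arm outcomes. That trace is faint, because dispatchers and tool are often both right or both wrong about which patient has the highest NEWS. It is also not specific: season, case mix, ties or the number of patients per RCS can move control outcomes without any spillover.

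A more direct measure is already stored, namely whether the control-arm ambulance went to the patient whom the hidden score ranked first. Item 3 of the same list follows compliance over time in the intervention arm, but nothing follows the matching quantity in the control arm.

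Item 4 is the only pre-specified analysis aimed at this bias. If the primary result is null, readers will ask whether the tool failed or the control arm was contaminated, and item 4 would usually be unable to help.

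**Working it through.** **Inputs**
- Control rate 63.5% and model rate 70.3% (Sample Size). The most that complete spillover could add is 70.3 − 63.5 = 6.8 points.
- "1500 RCS each consisting of multiple patients randomized 1:1 to control and intervention arms" (Abstract, Trial Size), so about 750 control RCS.
- Accrual of up to 2 years (Sample Size), taken as 24 equal months.
- Assumptions: two-sided alpha 0.05 for the slope, and a linear rise unless stated otherwise.

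**1. The plan's own figure.** Mean rate 0.669. SE under the null = √(2 × 0.669 × 0.331 / 750) = 0.0243. SE under the alternative = √((0.635 × 0.365 + 0.703 × 0.297) / 750) = 0.0242. Power = Φ((0.068 − 1.96 × 0.0243) / 0.0242) = Φ(0.84) = 0.80. The stated power reproduces.

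**2. Power of the control-arm slope.** For even accrual, the SE of the fitted rise over the whole trial is √(12 p(1−p) / n).
- Complete spillover: SE = √(12 × 0.669 × 0.331 / 750) = 0.0595; z = 0.068 / 0.0595 = 1.14; power = Φ(1.14 − 1.96) = 0.21. Simulated logistic regressions on month also give 0.21. One-sided at 0.05: Φ(1.14 − 1.645) = 0.31.
- Half spillover (63.5% to 66.9%): z = 0.56; power about 0.09 two-sided.
- The length of accrual does not matter: 12, 18 or 24 months all give about 21%.
- For 80% power the rise would have to be (1.96 + 0.84) × 0.0595 = 16.7 points, or the control arm about 750 × (2.80 / 1.14)² ≈ 4,500 RCS.

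**3. Other time shapes, complete spillover, two-sided**

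| Shape | Power |
|---|---|
| Step at mid-trial | 41% (42% simulated; 53% one-sided) |
| Ramp over the middle half | 35% |
| Step at 25% or 75% of the trial | 25% |
| Linear, later accrual weighted 2:1 | 19% |
| Saturating, 2-month time constant | 10% |
| Step at 10% of the trial | 8% |
| Complete from the start | no slope; false-positive rate only |

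**4. A more sensitive outcome.** The two-arm SE is √(2p(1−p)/n) and the slope SE is √(12p(1−p)/n), so a linear slope has the two-arm z divided by √6 = 2.45. An outcome with 95% two-arm power (z = 3.60) gives Φ(1.47 − 1.96) = 0.31. One with 99% (z = 4.29) gives Φ(1.75 − 1.96) = 0.42.

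**5. Agreement with the hidden mark.** The documents give neither baseline agreement nor compliance, so both are assumed. Complete spillover means that control agreement reaches intervention-arm compliance. The formula is that of step 2, with p at the mid-point. The last column assumes that outcome gain scales with agreement, so the rise is 6.8 × (compliance − baseline) / (1 − baseline) points.

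| Baseline → compliance | Complete | Half | Outcome slope, complete |
|---|---|---|---|
| 50% → 85% | >0.99 | 0.80 | 0.13 |
| 60% → 85% | 0.99 | 0.55 | 0.11 |
| 70% → 85% | 0.81 | 0.27 | 0.09 |
| 80% → 90% | 0.60 | 0.18 | 0.09 |

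For 80% → 90%: SE = √(12 × 0.85 × 0.15 / 750) = 0.0452; z = 0.10 / 0.0452 = 2.21; Φ(0.25) = 0.60. If the rise runs exactly from first month to last, z grows by 24/23 to 2.31 and power to 0.64. Simulation gives 0.64 to 1.00 for complete and 0.20 to 0.85 for half spillover. At the corner of 80% → 85%, z = 0.05 / 0.0481 = 1.04 and power is only 0.18, against about 0.06 for the outcome slope.

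**6. Why not arm × month.** Let control agreement stay flat at 60% while intervention compliance falls from 90% to 80%. Probability scale: z = 0.10 / √(0.0620² + 0.0452²) = 1.30, so Φ(1.30 − 1.96) = 0.26. Logit scale: the change is 0.81, the SE is √(12/(750 × 0.24) + 12/(750 × 0.1275)) = 0.44, z = 1.85, and power is about 0.46. Simulations gave 27% and 44%. Convergence would thus often be declared with no spillover.

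**7. Stakes.** Linear spillover lifts the control mean by 3.4 points, to 66.9%. Primary power becomes Φ((0.034 − 1.96 × 0.0240) / 0.0240) = Φ(−0.54) = 0.29.

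**The case against.** The strongest points on the other side are these.

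- **The 21% rests on choices that the plan does not make.** Item 4 is directional, states no alpha and does not restrict outcomes to the binary primary. Design defines outcome measures as score differences, and Sample Size says the difference-based test had power to spare. This stands as a limit on the single figure. Steps 2 to 4 show that power stays low under each alternative tried.
- **Control outcomes measure the bias itself.** The worry is a smaller estimated effect, and Outcomes deliberately prefers a yardstick independent of the model. This stands as a reason to keep the outcome slope. It does not make that slope informative when it is non-significant.
- **An agreement slope also misses constant spillover.** Carry-over through re-included patients could act from the first month. This stands, and it is why changing the dependent variable is not enough.
- **The gain may be modest.** If dispatchers already agree with the tool often, or comply with it only moderately, agreement has little room to rise. This stands: a reader might expect near-certain detection, and the documents cannot support that because neither quantity is given.
- **A null need not be misread.** A reader might infer that the plan will take a non-significant slope as proof of no spillover. No section says so. The inference is understandable, since spillover is defined by significance alone, but what the documents show is silence on how a null will be read.

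**Conclusion.** The point holds as a weakness of a supporting analysis; no primary or secondary test changes. On the protocol's planning rates and about 750 control RCS, item 4 has about 21% power for linear, complete spillover and about 9% for half. For the other shapes tried it reaches at most about 42% two-sided or 53% one-sided, and it has no power beyond its false-positive rate if spillover is constant from the start. These figures assume alpha 0.05, the primary outcome and 70.3% as the ceiling; quarterly model updating could move that ceiling.

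A reader might go further and conclude that the test will nearly always be non-significant. The mid-trial step contradicts that; low power is the supportable statement.

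Agreement with the stored mark was more sensitive in every scenario computed. The size of the gain is uncertain: roughly 0.6 to 1.0 for complete and 0.2 to 0.85 for half spillover in the four tabulated scenarios, and less if baseline agreement lies within a few points of compliance.

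**What to change.** In Hypotheses item 4 and in Statistical analysis:

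1. Make the main spillover measure control-arm agreement between the dispatched patient and the stored, undisplayed top-ranked patient. Estimate its slope on study month in the control arm, with a confidence interval, adjusted for number of patients and score gap.
2. Show intervention-arm agreement beside it for context. Do not use arm × month alone as the criterion.
3. As a check, re-score control RCS with the trial-start model, so that quarterly updating cannot move the measure.
4. Compare agreement in control RCS with and without a patient previously shown in an intervention-arm RCS. This addresses carry-over that produces no trend. The groups are not randomised and their sizes are not given, so use the same adjustment and treat the result as supportive.
5. Keep the control-outcome slope as descriptive with its confidence interval, and state that non-significance does not exclude spillover.

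The cost is SAP wording and a few lines of code on data already captured, with no added patients or procedures. The drawback is that agreement describes dispatcher behaviour and not the bias in the NEWS outcome, which is why the outcome slope should still be reported.

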#### Intervention

The intervention is based on a risk assessment instrument validated in a previous study. (1) Since the publication of the validation study, the risk assessment instrument been further developed to include free-text notes entered by dispatchers, which were found to improve the performance of the models. The full source code of the tool employed in the study is freely available for replication purposes: https://github.com/[name]/openTriage.

The framework estimates the likelihood that a patient will be assessed by ambulance crews to 1) have abnormal initial findings, 2) be transported to the hospital with lights and sirens, 3) receive a prehospital intervention, and 4) be admitted to the hospital, or die within 30 days. Hospital outcome measures are based on the first hospital visit within 72 hours to capture hospital visits of non-conveyed patients. The predicted likelihood for each of the outcomes is then combined into a composite risk score, with the above outcomes weighted 4:2:1:1. In each RCS included in the intervention arm, the patient with the highest composite risk score will be indicated in a user interface integrated in the Alitis dispatching system used in Uppsala and Västmanland. A graphical indicator of model confidence will be integrated in the user interface, notifying users as to whether the model has a high- or low level of confidence in the prediction, with a cutoff value calibrated to include ca. 50% of patients in each group.

Development of the modelling framework will be frozen upon initiation of the main study phase. New predictor and outcome data will however continue to be captured and used to update the models in a quarterly monitoring and model updating process to ensure patient safety.

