## Monitoring

All dispatch system data will be collected within a single IT infrastructure under the direct supervision of the PI. Outcome data will be collected either directly by the research group, or in close cooperation with the research group in the case of Västmanland. Randomly sampled outcome data will be manually checked to ensure quality. The research group will conduct regular follow-ups with dispatchers responsible for executing the study protocol to ensure compliance.

A data monitoring committee (DMC) consisting of the medical directorship of the ambulance services and dispatch centers in the two studied counties will handle adverse events (AEs) and make decisions regarding early trial stoppage. Early stopping will be evaluated quarterly based on the Haybittle–Peto rule, with a p-value of <0.01 bounding an effect regarding the primary hypothesis. (15) If this threshold is reached, the treatment group will be unblinded to determine if the effect is detrimental, in which case the study will be halted to ensure patient safety. No early stopping rule for a beneficial effect will be employed.

Theoretical model performance will be evaluated as part of the quarterly DMC reviews. If theoretical model performance is found to suffer from a significant reduction in performance during a given month, hyperparameter optimization will be attempted. If theoretical model performance degrades beyond the point at which a clinical benefit from the intervention can reasonably be expected, a decision by the DMC to pause the trial until the issues can be corrected may be taken. Any changes to model hyperparameters or the estimation framework will be noted in the manuscript, and be made available for peer- and public review.

The existing adverse event reporting system in both counties will be monitored by the DMC for AEs relating to the patients included in the trial. Any AEs reported by patients or providers will be evaluated by the DMC.

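### Pre-specified analysis 5 is labelled covariate drift, but a study-month slope on quarterly updated models describes the maintained tool and cannot separate drift from correction by updating

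*Combined protocol and SAP*

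**What the plan says.** All references are to the combined protocol and SAP.

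- **Hypotheses**, fifth of the six other pre-specified analyses: "Evaluation of change in risk assessment tool predictive value over time (covariate drift". The parenthesis names drift as the target.
- **Statistical analysis**, the only method given for it: "Pre-specified analyses 3-5 will be examined using time-series analysis within a regression framework employing a variable representing the study month". No term for model version or time since update is mentioned, and no scoring with a fixed model.
- **Intervention**: "Development of the modelling framework will be frozen upon initiation of the main study phase". The next sentence limits this: new predictor and outcome data continue to be captured and are "used to update the models in a quarterly monitoring and model updating process to ensure patient safety". What is frozen is development of the framework, not the fitted models.
- **Monitoring**: "If theoretical model performance is found to suffer from a significant reduction in performance during a given month, hyperparameter optimization will be attempted". Also: "Any changes to model hyperparameters or the estimation framework will be noted in the manuscript".
- **Flow** and **Data management / Collection**: risk scores are calculated and stored when the director compares the selected patients, in the control arm as well, and model predictions are kept in the dispatch database.
- **Sample Size**: data collection is capped at 2 years.
- **Setting** and **Data management / Collection**: Västmanland joins later than Uppsala, once outcome data are available to train and validate its models.

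**The concern.** A month slope measures drift only if the instrument being measured stays the same. Here the models change about every three months, and some changes may be made because performance has fallen. Two processes then act on the series in opposite directions: the population or its documentation moves away from the training data, and updating pulls the model back. Updating on a growing data set could also improve the models in its own right, which would offset drift further. Study month alone cannot separate these.

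What is at stake is interpretation. Under the drift label, a flat slope could be taken to mean that the setting is stable, when it may show only that updating worked. Anyone considering a model without such maintenance would want the first answer and would be given the second.

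**Working it through.** **Figures in the plan.** None is given for analysis 5. The one design figure that can be reproduced is the power of 0.8 for the primary test: 63.5% against 70.3%, 750 per arm and two-sided alpha 0.05 give 0.7997. It reproduces and plays no part in what follows.

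**Inputs.** From the documents: 24 study months (the 2-year cap) and an update every 3 months. Assumed: a constant loss of 1 unit per month for an unchanged model, and a fraction r of lost performance restored at each update. The documents give neither a drift size nor r, so r runs from 0 to 1.

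**Formula.** With months m = 0,…,23 (mean 11.5), the least-squares slope is Σ(m − 11.5)·y / Σ(m − 11.5)², and the denominator is 1150. The result is expressed as a share of the true monthly loss.

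**Two recovery models.**

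(a) Each update restores a fraction r of all loss accumulated so far. At r = 0.5 the loss just after successive updates is 1.5, 2.25, 2.625, …, levelling off at 3, so the series soon looks flat.

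(b) Each update restores a fraction r of that quarter's loss only. Then y = −m + 3r·floor(m/3). Since Σ(m − 11.5)·3·floor(m/3) = 1134, the visible share is 1 − r × 1134/1150.

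| r | (a) all accumulated loss | (b) that quarter's loss |
|---|---|---|
| 0 | 100% | 100% |
| 0.25 | 37% | 75% |
| 0.50 | 13% | 51% |
| 0.75 | 5% | 26% |
| 1 | 1.4% | 1.4% |

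At r = 1 both models give a sawtooth, y = −(m mod 3), with share 16/1150 = 1.4%.

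**What this does to detection.** Take as an example a 10-point fall between the first and last month in the proportion of RCS where the model marks the patient with the highest NEWS. Assume 1500 RCS spread evenly, a proportion near the plan's 70.3%, and a two-sided 5% test.

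- Standard error of the slope: √(0.703 × 0.297/1500)/6.922 = 0.00170 per month, where 6.922 = √(1150/24).
- True slope: 0.10/23 = 0.00435 per month, so z = 2.55 and power is about 72% with a fixed model.
- At r = 0.5, z = 2.55 × 0.132 = 0.34 under (a) and 2.55 × 0.507 = 1.29 under (b), with power about 6% and 25%.
- At r = 1, power is about 5%, the significance level.

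**Can terms for updating rescue the deployed series?** In this noise-free illustration, regression on version indicators plus months since update returns the full drift slope at every r, under both models. Two limits apply. With regular quarterly updates, month is an exact linear combination of the version indicators and time since update, so all three cannot be fitted together. The within-version slope also rests on only three months per version: its sum of squares is 8 × 2 = 16 against 1150, so its standard error is √(1150/16) ≈ 8.5 times larger. Scoring everyone with one fixed model corresponds to r = 0 and keeps the full precision.

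**The case against.** The strongest reply is that the tool under trial is the updated tool. Quarterly updating is part of the intervention as described, and a month slope on deployed scores says correctly whether that tool held its predictive value. This stands. A reader might infer that analysis 5 cannot answer any useful question; the documents do not support that. It answers the question of maintained performance and fails only under the drift label.

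Second, the plan does not say that analysis 5 uses deployed scores only, and naming month as "employing a variable representing the study month as the independent variable of interest" does not exclude other terms. This also stands, so the point is conditional. Deployed scores remain the natural reading because those are the scores stored at each comparison, and no rescoring or version term is mentioned anywhere.

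Third, a reader might infer that the investigators would report that the tool needs no maintenance. No section plans such a conclusion. The protocol takes maintenance for granted, has performance reviewed quarterly, and promises to report changes. That promise covers hyperparameters and the estimation framework; it does not name the routine quarterly updates, and disclosure is not an adjustment in the analysis.

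Fourth, a reader might infer that the planned regression would hide nearly all of the drift. That does not follow. Near-total masking needs either full recovery or substantial recovery of all accumulated loss. At 25% recovery, between 37% and 75% of the slope stays visible, and if updates restore nothing the slope is unaffected. Full recovery is also doubtful: the training outcomes include death within 30 days, so the most recent outcomes may be incomplete at an update.

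Finally, a model fixed at the start of the main phase may have no Västmanland training data, so a pooled fixed-model slope would mix that centre's entry with drift. This is right, and the fix has to deal with it.

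**Conclusion.** The point holds in conditional form. If analysis 5 is run on deployed scores, the study-month slope is the net performance of the maintained tool. It cannot separate drift from correction by updating, and a flat slope is not evidence that drift is absent.

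The size cannot be fixed from the documents. Under linear drift over 24 months with updates every 3 months, the visible share of the true slope is 100% with no recovery, 37–75% at one-quarter recovery, 13–51% at half, 5–26% at three-quarters and about 1% at full recovery. The ranges reflect whether an update restores a share of all accumulated loss or only of the latest quarter's. These are illustrations, not estimates for this trial.

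The point concerns one additional pre-specified analysis. It does not touch the primary or secondary hypotheses, the sample size or the safety monitoring. It is worth acting on because the better analysis is cheap.

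**What to change.** 1. Archive the model in use at the start of the main phase, and each later version with its dates of use.
2. Rescore RCS patients offline with the fixed model, using the captured predictors as they stood when the comparison was made. Run the month regression on these scores as the drift analysis.
3. Do this within centre: Uppsala from the start, and Västmanland from its entry with the first model version used there, or include a centre term.
4. Report the month regression on deployed scores separately, under the name of performance of the maintained tool. Accompany it with a model containing version and time-since-update terms. If version enters as indicators, leave month out of that model because of the exact collinearity shown above.
5. If fixed-model rescoring is not possible, relabel analysis 5 as performance of the updated tool and drop the drift interpretation.

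The cost is some archiving, offline rescoring and a few sentences in the Statistical analysis section. Live updating and the handling of patients do not change.
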